10.0 Local Number of Participants

PROTOCOL TITLE: Does Social Buffering Continue to be Effective Over the Peripubertal Period
When Friends Share the Stressor Experience?

VERSION DATE: v.3.3 3.31.23

10.1 Local Number of Participants to be Consented: We plan to analyze at least 200 target participants. Of those 50 will participate alone, while 150 will participate with a social peer. Social peers will be enrolled as they will at least complete a questionnaire. Thus, we will enroll at least 350 children. To account for attrition between sessions/replacement for incomplete data, we anticipate up to 400 children may be enrolled.

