14.2 Power Analysis: For the power analysis for the primary analyses, we calculated the minimum detectable effect size (MDES) assuming $n = 200$, $\alpha = .05$, and power = .80 with a conservative estimate of 12 covariates in our model (see section 4.3). Power was calculated in R (R Core Team, 2018) using the pwr library (Champely, 2018). A power analysis was performed to quantify the MDES (measured as f^2) for a three-way interaction between the social buffering condition, sex, and pubertal stage within a multiple regression model controlling for all potential covariates, two-way interactions, and main effects (the most complex model considered in our primary analysis, see equation 1 below). Assuming these conditions, we should be able to detect an f^2 of 0.056. In other words, adding the three-way interaction to a model containing the covariates and all lower order interactions and main effects, the three-way interaction would need to explain an additional 5.6% of the variability to be detected. This falls between Cohen’s criteria for a small ($f^2 = .02$) and medium-sized effect ($f^2 = .15$) (Cohen, 1988). With a sample size of 200, even if we lost 40 of the participants, assuming all the previous conditions except a sample size of 160, we would still be power enough to detect an f^2 of .070, or still within a small-medium effect size. As the number of covariates decreases, the size of the MDES will decrease. Therefore, this represents a conservative estimate of power for our primary analyses as we are likely to have fewer covariates in our models and will use multiple imputation to correct for missing data. For the two-way interaction and main effects models, described below, the power will be larger than these reported values as the

PROTOCOL TITLE: Does Social Buffering Continue to be Effective Over the Peripubertal Period
When Friends Share the Stressor Experience?

VERSION DATE: v.3.3 3.31.23

models will be simpler. In addition, we ran a power analysis that corrected for multiple comparisons using the conservative Bonferroni's adjustment. Because we expect to run 9 independent multiple regression models or fewer, we ran our models assuming an alpha of 0.05 / 9. Based on this reduced alpha, we expect to be able to detect an effect of .07.

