14.3 Statistical Analysis: The primary analyses will consist of a series of multiple regression models. For each dependent variable, Cortisol AUCi, Alpha-Amylase AUCi, we will begin by testing the three-way interaction between social buffering condition, sex, and pubertal stage for all outcomes. If the three-way interaction is not significant, we will then examine all two-way interactions. If the two-way interactions are not significant, we will then examine main effects only models. If the three-way interaction is significant, we will not examine any other model.

14.4 Data Integrity: *Multiplicity of testing.* We will correct for multiple comparisons using the Benjamini-Hochberg (BH) correction. The BH method works by controlling the false discovery rate, and relative to the Bonferroni's correction is more powerful, while still adequately protecting against Type I errors (Williams et al., 1999).

Missing data. If there is missingness in any of the dependent or independent variables, multiple imputation will be used (Little & Rubin, 2014; Peng et al., 2006; Schafer & Graham, 2002). Variables related to the missingness and the variables missing data will be included in the missing data model. In the event that missingness is not at random (MNAR), we will investigate the use of models for non-ignorable missing data.

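### The imputation rule in 14.4 does not require the product terms of the interaction that 14.3 tests first; if they are omitted, that test is attenuated and loses power

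*Combined protocol and SAP*

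**What the plan says.** Section 14.4 (Missing data) applies multiple imputation whenever an outcome or predictor is missing. Its only instruction on the content of the imputation model is: "Variables related to the missingness and the variables missing data will be included in the missing data model". It names no analysis variable and no product term.

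Section 14.3 says of the primary outcomes, cortisol AUCi and alpha-amylase AUCi: "we will begin by testing the three-way interaction between social buffering condition, sex, and pubertal stage for all outcomes". If that test is not significant, the analysis moves to two-way models and then to main effects.

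Section 14.2 powers this interaction "within a multiple regression model controlling for all potential covariates, two-way interactions, and main effects". It also considers a loss scenario ("even if we lost 40 of the participants, assuming all the previous conditions except a sample size of 160"). It then gives the use of multiple imputation as one of two reasons for calling its power estimate conservative.

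Section 10.1 adds: "We plan to analyze at least 200 target participants". It allows extra enrolment for attrition and for replacing incomplete data. No expected rate of missing outcomes is given anywhere.

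**The concern.** An imputation model should be at least as rich as the model fitted afterwards. If AUCi is imputed from a model without the three-way product, the imputed values are generated as though that interaction were zero. Mixing them with observed values dilutes the estimate.

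The rule can be read in two ways:

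- **Variables related to missingness, plus the incomplete variables.** Condition and sex, which should be complete, then enter only if they happen to predict missingness.
- **Variables related to missingness or to the incomplete variables.** Condition, sex and stage then enter, as main effects, if they relate to AUCi.

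Neither reading calls for the products.

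The stakes come from the testing sequence. The three-way test decides which model is reported, so a diluted interaction can send the analysis to a simpler model and suggest that buffering does not depend jointly on sex and puberty.

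**Working it through.** **Inputs from the plan.** n = 200, four equal conditions randomised within four sex-by-puberty strata, stage continuous (14.1); alpha 0.05, power 0.80, 12 covariates, f² = 0.056, loss of 40 (14.2). **Assumption:** 5%, 10% or 20% of outcomes imputed.

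**The plan's own figure.** The power formula is a noncentral F with λ = f²(u + v + 1). Four conditions give u = 3. With v = 200 − 4 = 196, λ = 0.056 × 200 = 11.2 and power is 0.803, so 0.056 is reproduced (minimum detectable f² 0.0556). Likewise 0.070 is reproduced at n = 160 with v = 156 (0.0699). Deducting the 15 model terms and 12 covariates gives v = 200 − 1 − 27 = 172, power 0.744 and a minimum detectable f² of 0.063. That is a separate matter. Here f² = 0.056 serves only as the true effect.

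**Analysis model.** Intercept 1, main effects 3 + 1 + 1 = 5, two-way terms 3 + 3 + 1 = 7, three-way terms 3, total 16 parameters. With complete data and no covariates, v = 200 − 16 = 184 and λ = 11.2 give power 0.80.

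**Expected shrinkage.** If a fraction m of outcomes is imputed with zero interaction, the pooled estimate is about (1 − m) × true + m × 0. That is 0.95, 0.90 and 0.80 of the true effect at m = 5%, 10% and 20%.

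**Simulation.** n = 200, true f² = 0.056 or close to it (full-data power about 0.80), no covariates, no auxiliary variables, normal-model imputation of the outcome, 20 imputations, pooled 3-df Wald test at 0.05. Ranges span runs with slightly different settings, mostly 1,500 to 4,000 replicates each.

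| Outcomes missing | Effect kept, three-way product omitted | Power, product omitted | Power, all terms included | Power, complete cases |
|---|---|---|---|---|
| 5% | 93–94% | 0.69–0.73 | 0.78–0.79 | 0.78 |
| 10% | 88–90% | 0.59–0.66 | 0.73–0.76 | 0.74–0.77 |
| 20% | 76–80% | 0.34–0.43 | 0.63–0.68 | 0.67–0.69 |

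With all terms included, about 99–100% of the effect is kept.

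**Which omission matters.** At 20% missing, power was about 0.40 with main effects only in the imputation model and about 0.38 with main effects plus two-way terms. Adding lower-order terms does not help. The three-way product is decisive.

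**Missingness that differs by condition** (5% in one condition, 25% in three; (5 + 3 × 25)/4 = 20% overall). Product omitted: 75% of the effect kept, power 0.35. All terms: 101%, power 0.66.

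**Under no interaction**, same missingness: rejection was about 1% with the product omitted, 5.5% with all terms and 5% with complete cases. The pooled variance is then too wide, which is why power falls by more than the shrinkage alone would suggest.

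**Auxiliary variables.** A further check at 20% missing (800 replicates) imputed from main effects plus one auxiliary correlated with AUCi. The effect kept was 0.79 without the auxiliary and 0.86, 0.89 and 0.97 at assumed correlations of 0.5, 0.7 and 0.9. At 10% missing it was 0.94–0.97 with the auxiliary.

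**The case against.** A reader might infer that 14.4 excludes condition, sex and stage, so that the primary test is certain to be biased. The text does not support that. It is an inclusion rule without the word 'only', it can be read in two ways, and a careful analyst could add every term without departing from it. Stage is self-reported (5.2) and may itself be incomplete, which would bring it in. Condition may predict missingness, since three of the four conditions need a second child online. These points stand, but they bring in main effects, and main effects do not cure the problem.

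A reader might also take 20% as the plan's expected imputation rate. It is not: "even if we lost 40 of the participants" is evaluated at a sample size of 160, as lost participants, and planned replacement (10.1) points to fewer imputed outcomes. That stands, so 20% is only the upper end of an assumed range. At 5% the loss is small.

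The simulations use no auxiliary variables, whereas saliva is taken several times and remaining samples could carry much of the signal. That stands for a youth missing one sample. It helps much less for one who provides none, and sections 17.1 and 19.1 let participants skip tasks or stop.

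Finally, the error is conservative. That stands too: there is no false-positive risk, and the cost falls on estimation and power.

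**Conclusion.** The concern holds as a gap in the rule: 14.4 does not require the terms that the first primary test depends on. It is not established that they will be left out.

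If the products are omitted without a strong auxiliary, the interaction shrinks roughly by the fraction of outcomes imputed. Comparing within runs, power is lower than with a full imputation model by about 0.05–0.10 at 5% missing, 0.10–0.15 at 10% and 0.25–0.29 at 20%. It is also below complete cases. This undercuts the reassurance in 14.2. In these simulations even full-model imputation only matched complete cases, and imputation without the products did worse.

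The figures rest on assumed missing rates, a true f² of about 0.056, normal outcomes, no covariates and missing outcomes only. Missing pubertal stage was not simulated. The gap should be closed before analysis.

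**What to change.** Replace the rule in 14.4 with wording such as: the imputation model will contain every term of the 14.3 primary model (condition, sex, pubertal stage, all two-way and three-way products, and retained covariates) plus variables related to missingness. An acceptable alternative is to impute within condition-by-sex cells (200/8 = 25 each) with stage as a predictor.

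As a consequence, 14.2 should no longer count imputation as a reason its power estimate is conservative unless useful auxiliary variables are named. Complete-case results could optionally be reported as a sensitivity analysis.

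The cost is a sentence or two of plan text and slightly longer imputation code. No new data are needed.

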15.0 Confidentiality

15.1 Data Security:

Only authorized research staff will have access to the data, and all data will be stored on encrypted servers or locked locations. Birth date will be maintained in order to ensure the correct age of the participant at the time of participation. However, this will be deleted once age at participation is obtained. In addition, recordings of the TSST session must be kept in order to code for participant, friend behaviors. Recordings and birth date will only be linked with participant ID number.

A password-protected document linking name and ID number will be kept until the conclusion of the study in case we must contact a family for any reason. We will use REDCap for this. This document will be destroyed at the conclusion of the study.

Password protection is used to protect data files. Because this session will be conducted online, we anticipate that all experimenter, parent, and youth reports will be completed on REDCap, and stored there or on

PROTOCOL TITLE: Does Social Buffering Continue to be Effective Over the Peripubertal Period
When Friends Share the Stressor Experience?

VERSION DATE: v.3.3 3.31.23

University Box. No consent/assent will be placed in participants' medical, employment, or educational records.

16.0 Provisions to Monitor the Data to Ensure the Safety of Participants

16.1 Data Integrity Monitoring.

All of the proposed procedures meet the NIH definition of minimal risk. The PI and study coordinator will meet regularly to ensure that study protocols are followed and best practices are applied. Study coordinator will bring any identified protocol violations to the PI in a timely fashion, and members will be re-trained if needed.

16.2 Data Safety Monitoring.

Overall Framework for DSMP

This project is considered a clinical trial because it involves a) random assignment to condition, and b) physiology is being measured.

There is no risk associated with the assignment to conditions (Close Friend-Both Tested, Unfamiliar Peer-Both Tested, Close Friend-Social Support Only, No Partner). All conditions resemble naturally occurring social situations that children might experience, and there is no inherent danger to one condition over another as there would be for, say, a drug vs placebo trial.

Further, in three of the conditions the presence of another person is expected to provide a social buffer whose stress reduction potency by condition is what is being tested. All target youth experience the same stressor, the TSST. The TSST mimics a naturally occurring stressor, as when the youth is asked to speak in front of the class and his/her performance is being evaluated. This can provoke anxiety.

The other potential risks of this study to which all of the participants are exposed regardless of condition have been eliminated in this online-only revision.

The steps taken to reduce or prevent these risks include allowing participants to refuse the nurse exam and use of proper saliva collection materials. These risks are all managed by the routine processes monitored by our IRB, including Serious Adverse Events (SAEs) such as deaths, hospitalizations, and life threatening events and Unanticipated Problems (UPs), will be managed and reported, as required, to the IRB and relevant monitoring authorities. All members of the project will have received human subjects training and certification in FDA Good Clinical Practice through the Collaborative Institutional Training Initiative (CITI) curriculum.

PROTOCOL TITLE: Does Social Buffering Continue to be Effective Over the Peripubertal Period
When Friends Share the Stressor Experience?

VERSION DATE: v.3.3 3.31.23

The individuals responsible for trial monitoring and advising the appointing entity. Because of the low level of risk in this study, the PI, [name] will be responsible for reporting.

17.0 Provisions to Protect the Privacy Interests of Participants

17.1 Protecting Privacy: Once the participant has been tested, identifying information will be removed, and all materials will be identified with a participant number only. A master list with participant names, addresses and contact information will be maintained on REDCapseparately from the data and study materials. Only researchers involved in the study will have access to the data and the file that merges participant number and personal information.

Considerable efforts are made to make participants comfortable, despite the nature of the stressor in the second session. Consent and all study procedures will be conducted in private, tho online, rooms. During consent/assent multiple efforts are made to make it clear that participation is optional and the youth is in control of refusal. (Because cards will be mailed empty to prevent possible theft, cards will be loaded after the session is complete. However, we would not withhold payment to a participant who began a session and ended it due to discomfort. !)
Collection of biological measures, administration of sensitive questionnaires are all done with a “matter of fact” attitude to minimize any feeling of embarrassment. Should a participant need to skip a portion or end a session early, experimenters are trained to accept this as a standard procedure when working with children rather than a problematic ending to the session. We have successfully guided hundreds of youth through these very procedures without undue problem, including longitudinal studies where the participants continue to return.

17.2 Access to Participants: We do not access medical records or other sources of private information.

18.0 Compensation for Research-Related Injury

18.1 Compensation for Research-Related Injury: All of the proposed procedures meet the NIH definition of minimal risk.

18.2 Contract Language: NA

19.0 Consent Process

19.1 Consent Process (when consent will be obtained):

-
- The consent process begins at recruitment. A full consent will occur online over Zoom, where we have been able to interact with them

PROTOCOL TITLE: Does Social Buffering Continue to be Effective Over the Peripubertal Period
When Friends Share the Stressor Experience?

VERSION DATE: v.3.3 3.31.23

privately in our experience. We control the environment at our end, and all staff take care to maintain a private environment. We send the consent to parents following recruitment, so that participants have typically 1-3 weeks to consider, before the online session and the full consent process.

- Researchers are trained and experienced consenters follow scripted protocols to determine that a potential participant understands the information. Open ended questions are gently used to assess understanding, for example, “can you tell me what we will do today?”
- At consent/assent, we make it clear that participation can end without negative consequences. Children are told that they can skip any task or stop the session as needed.
- Consent & Assent will be documented over REDCap.

19.2 Waiver or Alteration of Consent Process (when consent will not be obtained): N/A

19.3 Waiver of Written/Signed Documentation of Consent (when written/signed consent will not be obtained): N/A

19.4 Non-English Speaking Participants: N/A

19.5 Participants Who Are Not Yet Adults (infants, children, teenagers under 18 years of age):

- All participants will be children, recruited by contacting parents. Age will be verified with parent.
- Parental permission will be obtained from:
 - One parent, even if the other parent is alive, known, competent, reasonably available, and shares legal responsibility for the care and custody of the child.
- In the case of the “friend” to the target participant, we will obtain consent/assent by phone/email or Zoom. If we lack parental consent, that session converts to “alone”, but if we merely lack assent, we will obtain that at the online TSST session, and include a line for target parent’s signature as witness.
- All youth will be part of the consent process, will be asked questions to verify understanding, including the question of “when will you be allowed to skip a task or end the session?”, and will sign an assent form.

19.6 Cognitively Impaired Adults, or adults with fluctuating or diminished capacity to consent:

- NA

19.7 Adults Unable to Consent:

PROTOCOL TITLE: Does Social Buffering Continue to be Effective Over the Peripubertal Period
When Friends Share the Stressor Experience?

VERSION DATE: v.3.3 3.31.23

- NA

20.0 Setting

20.1 Research Sites:

- Participants will be recruited from the ICD registry of potential participants, or self-identified thru flyer/website.
- Research will be conducted online, using HIPAA-Compliant Zoom and REDCap.

20.2 International Research: NA

21.0 Multi-Site Research

NA

22.0 Resources Available

22.1 Resources Available:

- There are sufficient potential participants on the registry to meet the needs of the study design/cell count. In the age range we would need over the years of this proposal there are 14,529 girls and 15,284 boys from which to draw.
- We anticipate it will take approximately 2 years to complete recruitment and testing.
- We do not anticipate the need for either medical or psychological resources that participants might need as a result of anticipated or unanticipated consequences of the research, as risk is minimal. However, Drs [name] & [name] are widely connected to such resources at the University.
- All staff & lab personnel, including undergraduate students working with de-identified data, undergo required and available ethics training, and PI [name]'s lab manager has over 25 years of experience training staff and conducting research with children. Weekly project meetings keep us adequately informed about the protocol, the research procedures, and their duties and functions.

